	Withdrawal, as manifested by either of the following: a) The characteristic withdrawal syndrome for alcohol b) Alcohol is taken to relieve or avoid withdrawal symptoms	6	Continued alcohol use despite having persistent or recurrent social or interpersonal problems caused or exacerbated by the effects of alcohol. (See DSM-IV, criterion 4.)	
	Alcohol is often taken in larger amounts or over a longer period than was intended.	7	Important social, occupational, or recreational activities are given up or reduced because of alcohol use. (See DSM-IV, criterion 10.)	
	There is a persistent desire or unsuccessful efforts to cut down or control alcohol use.	8	Recurrent alcohol use in situations in which it is physically hazardous. (See DSM-IV, criterion 2.)	
	A great deal of time is spent in activities necessary to obtain alcohol (e.g., driving long distances), use alcohol, or recover from its effects.	9	Alcohol use is continued despite knowledge of having a persistent or recurrent physical or psychological problem that is likely to have been caused or exacerbated by alcohol. (See DSM-IV, criterion 11.)	
	Important social, occupational, or recreational activities are given up or reduced because of alcohol use.	10	Tolerance, as defined by either of the following: a) A need for markedly increased amounts of alcohol to achieve intoxication or desired effect b) A markedly diminished effect with continued use of the same amount of alcohol (See DSM-IV, criterion 5.)	
	Alcohol use is continued despite knowledge of having a persistent or recurrent physical or psychological problem that is likely to have been caused or exacerbated by the substance (e.g., continued drinking despite recognition that an ulcer was made worse by alcohol consumption).	11	Withdrawal, as manifested by either of the following: a) The characteristic withdrawal syndrome for alcohol (refer to criteria A and B of the criteria set for alcohol withdrawal) b) Alcohol (or a closely related substance, such as a benzodiazepine) is taken to relieve or avoid withdrawal symptoms. (See DSM-IV, criterion 6.)	
				The presence of at least 2 of these symptoms indicates an Alcohol Use Disorder (AUD) .
				The severity of the AUD is defined as: Mild: The presence of 2 to 3 symptoms Moderate: The presence of 4 to 5 symptoms Severe: The presence of 6 or more symptoms

### Appendix B: Schedule of Study Procedures

	Pre-Screening	Screening	Refresher Screening	Baseline	Treatment Phase						Follow Up	
Visit #	-1	1	1	2	3	4	5	6	7	8	9 F-UP	10 F-UP
		1 to 28 days before visit 2	Only to be run if 28 days elapses between screening and visit 2	1 to 28 days after screening	1 to 5 days after visit 2	4 to 21 days after visit 2	1 to 5 days after visit 4	4 to 21 days after visit 4	1 to 5 days after visit 6	4 to 21 days after visit 6	11 to 13 weeks after visit 2	23 to 25 weeks after visit 2
Trial discussion with Participant	X	X	X									
Pre Screening Questionnaire	X											
Informed Consent		X										
Medical History		X	X									
Physical a		X	X									
SCID		X	X								X	X
Vital Signs b		X	X	X	X	X	X	X	X	X		
Bloods c, d		X c	X	X d	X d	X d	X d	X d	X d	X d	X d	X d
Eligibility determination	X	X	X	X								
Urine Drug screen		X e	X	X e	X f	X e	X f	X e	X f	X e	X e	X e
Pregnancy Test I WOCBP		X	X	X		X		X				
Breathalyser		X	X	X	X	X	X	X	X	X	X	X
Randomisation				X								
SCRAM-X fitting		X g	X g	X g								
IMP/Plac administration				X		X		X				
SCRAM-X checks			X	X	X	X	X	X	X	X		
Relapse-prevention based CBT				X	X	X	X	X	X	X		
Adverse Events review				X	X	X	X	X	X	X	X	X
Concomitant Medication review		X	X	X	X	X	X	X	X	X	X	X
Alcohol and Drug Use		X	X							X	X	X

History												
---------	--	--	--	--	--	--	--	--	--	--	--	--

Visit #	Pre-Screening	Screening	Refresher screening	Baseline	Treatment Phase						Follow Up	
	-1	1	1	2	3	4	5	6	7	8*	9* F-UP	10* F-UP
		1 to 28 days before visit 2	Only to be run if 28 days elapses between screening and visit 2	1 to 28 days after screening	1 to 5 days after visit 2	4 to 21 days after visit 2	1 to 5 days after visit 4	4 to 21 days after visit 4	1 to 5 days after visit 6	4 to 21 days after visit 6	11 to 13 weeks after visit 2	23 to 25 weeks after visit 2
BDI		X	X	X		X		X		X	X	X
HAM-D		X	X	X	X	X	X	X	X	X	X	X
Columbia Suicide Severity Rating Scale		x	X									
POMS				X	X	X	X	X	X	X	X	X
Reasons for Drinking Questionnaire		X										
STAI		X		X		X		X		X	X	X
ACQ-NOW		X		X	X	X	X	X	X	X	X	X
BPRS		X	X	X	X	X	X	X	X	X	X	X
PSI		X	X	X		X		X		X	X	X
Alcohol Timeline Follow Back		X	X	X		X		X		X	X	X
Drink diary										X	X	X
Fagerstrom Nicotine Dependence				X						X	X	X
Craving VAS				X	X	X	X	X	X	X	X	X
SF-12				X						X	X	X
Prose Recall				X	X	X	X	X	X	X	X	X

Delay Discounting (monetary choice questionnaire)				X						X	X	X
Stop Signal Reaction Time				X						X	X	X
Working Memory (digit span WAIS-IV)				X						X	X	X
Adverse effects VAS +				X	X	X	X	X	X	X	X	X
Pattern Recognition Memory Test				X		X		X		X	X	X

Performed by Research Fellow, Nurse or Assistant

Performed by Anaesthetist

\* In the week prior to Visits 8, 9 and 10 patients will be telephoned to remind them of their attendance.

- a) Physical – Height, weight, An examination of cardiovascular, respiratory, GI and neurological function to a level of detail that would be expected for a patient due to receive anaesthesia.
- b) Vital signs: oral/tympanic temperature, resting pulse, pulse oximetry and Blood Pressure.
- c) Bloods (Screening) – FBC (haemoglobin, white cell count, platelets, mean red cell volume); Liver function (Bilirubin, ALT, AST, Total Protein, Alkaline Phos (ALP), Albumin, Globulin, gamma-glutamyl transpeptidase (GGT)), Biochemistry (urea, sodium, potassium, glucose, calcium, thyroid stimulating hormone).
- d) Bloods (Study): BDNF; ketamine; Liver function (Bilirubin, ALT, AST, Total Protein, Alkaline Phos (ALP), Albumin, Globulin, gamma-glutamyl transpeptidase (GGT)).
- e) Urine Drug screen (Screening, infusion days and F-UP visits) - (methamphetamine, cocaine, THC, benzodiazepines, tricyclic antidepressants, barbituates, phencyclidine, amphetamines, morphine, methadone, ketamine).
- f) Urine Drug screen (Non-infusion days, treatment phase) – (methamphetamine, cocaine, THC, benzodiazepines, tricyclic

antidepressants, barbituates, phencyclidine, amphetamines, morphine, methadone).  
g) SCRAM-X device can be fitted at any one of these visits.

## Appendix C: Known Adverse Effects of Ketamine when used in an anaesthetic setting

The following Adverse Events have been reported:

MedDRA System Organ Class	Frequency†	Undesirable Effects
Immune system disorders	Rare	Anaphylactic reaction*
Metabolism and nutrition disorders	Uncommon	Anorexia
Psychiatric disorders	Common	Hallucination, Abnormal dreams, Nightmare, Confusion, Agitation, Abnormal behaviour
	Uncommon	Anxiety
	Rare	Delirium* Flashback*, Dysphoria*, Insomnia, Disorientation*
Nervous system disorders	Common	Nystagmus, Hypertonia, Tonic clonic movements
Eye disorders	Common	Diplopia
	Not Known	Intraocular pressure increased
Cardiac disorders	Common	Blood pressure increased, Heart rate increased
	Uncommon	Bradycardia, Arrhythmia
Vascular disorders	Uncommon	Hypotension
Respiratory, thoracic and mediastinal disorders	Common	Respiratory rate increased
	Uncommon	Respiratory depression, Laryngospasm
	Rare	Obstructive airway disorder*, Apnoea*
Gastrointestinal disorders	Common	Nausea, Vomiting
	Rare	Salivary hypersecretion*
Hepatobiliary disorders	Not known	Liver function test abnormal, Drug-induced liver injury**

Skin and subcutaneous tissue disorders	Common	Erythema, Rash morbilliform
Renal and urinary disorders	Rare	Cystitis*, Haemorrhagic cystitis*
General disorders and administration site conditions	Uncommon	Injection site pain, Injection site rash

† Common ( $\geq 1/100$  to  $< 1/10$ ); Uncommon ( $\geq 1/1,000$  to  $< 1/100$ ); Rare ( $\geq 1/10,000$  to  $< 1/1,000$ ); Not known (frequency cannot be estimated from the available data)

\* AE frequency estimated from post-marketing safety database

\*\* Extended period use (>3 days) or drug abuse

The KARE trial is a phase-II randomised trial comparing an active drug intervention (ketamine) with a placebo (saline), and comparing psychotherapy with no psychotherapy (alcohol education). This trial is funded by the Medical Research Council (MRC), and sponsored by University College London (UCL), Sponsor number 13/0253. The EudraCT reference number is 2015-000222-11. The trial has been approved by the South West – Central Bristol Research Ethics Committee (reference number: 15/SW/0312).

This trial aims to gather data regarding the clinical effectiveness of intravenous ketamine (with and without a concurrent psychotherapy intervention) with regard to prevention of relapse (recommencing alcohol use) in participants who are currently abstinent, but who have a current diagnosis of alcohol dependence. The trial will also gather data regarding safety and tolerability of ketamine, and assess compliance with the drug and psychotherapy interventions. Full details of the trial are set out in the KARE trial protocol, Final Version 12, dated 20.01.2020. This statistical analysis plan (SAP) is written in relation to this protocol.

Participants are randomised individually to their combination of ketamine/placebo and psychotherapy/psychoeducation control using a blocking design. Participants are aware of all available treatment options, and that they could potentially be allocated to any of these. The drug intervention is administered by an anaesthetist who is blinded to the drug intervention allocation and also to the therapy intervention. The psychotherapist cannot be blinded to the therapy intervention, but is blinded to the drug intervention. The patient is also blinded to the drug intervention, but is aware of whether they receive psychotherapy or control.

4. Trial information

4.1 Interventions

KARE has two forms of intervention, a drug intervention and a psychotherapy intervention. The active drug intervention is ketamine, an anaesthetic/analgesic drug, to be administered intravenously. The placebo control

is saline. As well as a drug intervention the participants will receive concurrently either a psychotherapy intervention, or a psychoeducation control intervention. Hence, there are four combinations: (i) ketamine + psychotherapy; (ii) ketamine + psychoeducation; (iii) placebo + psychotherapy; (iv) placebo + psychoeducation. Participants will receive their allocated drug infusion in 3 doses over 3 weeks. Participants will concurrently receive either psychotherapy or psychoeducation control. The trial will be performed at two sites: Devon (Royal Devon & Exeter Foundation NHS Trust) and London (UCLH).

4.2 Phase of trial

KARE is a Phase II clinical trial (a proof of concept study/feasibility study).

4.3 Randomisation level

Randomisation will be performed by an independent organisation, Sealed Envelope, that specialises in randomisation and online databases for clinical trials (<https://www.sealedenvelope.com/>). Participants are randomised individually. To aim for balance across the four treatment combinations, a block randomisation will be performed (block sizes are known only to the trial statistician and the designated staff at Sealed Envelope). Randomisation will be performed separately for each site. A list of randomisation allocation codes will be generated in advance by Sealed Envelope, with each code indicating the drug allocation (ketamine or placebo) and the psychotherapy intervention (psychotherapy or psychoeducation). These codes will be sent to the trial statistician, who will generate two envelopes for each participant, one indicating the drug allocation and the other indicating the psychotherapy intervention. These envelopes will be securely delivered to trial staff at each site. The trial unblinded research nurse will receive the drug allocation envelopes for the Devon site, and the hospital pharmacist at UCLH. The trial psychologists at each site will receive the psychotherapy allocation envelopes for the Devon and London sites. When recruited by trial researchers, the participant's data will be entered to the online eCRF database. The participant will be allocated a trial ID number. The randomisation will be performed using the online eCRF database by the trial anaesthetist at each site. This trial ID number will be linked to the next available randomisation allocation code, and this information will be sent via email to the relevant member of the trial team so that they can open the participant's envelope to discover their randomised allocation.

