## 6 Recruitment

The patients will be primarily recruited through Participant Identification Centres. These centres will be the substance misuse and addiction psychiatry services in Central, North West, South London as well as Devon, Dorset, Wiltshire, Somerset and Bristol who will refer potential participants to the research team. Avon and Wiltshire PIC will also distribute their “Everyone Included” letter, a research opportunity letter, to potentially eligible participants. The principal and co -investigators will work to raise awareness and educate all addiction service providers about the study. Based on previous experience, we expect that recruitment of suitable patients will primarily occur by being identified by their Doctor, nurse or other professional in the clinic or service they are attending. Patients will also be recruited from primary care (GP practices) with the aid of Clinical Commissioning Groups (CCGs) in the South West and London. PICs will be provided with a recruitment flyer that can be distributed amongst staff that are advertising the trial to potential participants to help them remember the key aspects of the trial, e.g. basic inclusion/exclusion criteria, and facilitate discussion. If interested, the patient/user will be given a REC approved invitation to participate letter, giving a brief description of the study and the contact details of the study team. Patients may contact the study team themselves, or complete the return slip and agree that their name and contact number can be given to the research fellows. The research team will then ensure the patient receives the Patient Information Sheet, via post, email or via the study team and follow up the patient with a telephone call to further discuss the study and conduct a pre-screening assessment (see section 7.4).

The research fellow / assistant psychologist will then contact the individual interested in participating via phone and discuss the trial and answer any queries they may have. If they would like to participate, the researcher will

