then go through the prescreening questionnaire to establish whether the patient appears eligible to attend for a full screening appointment. If the patient appears eligible, the researcher will arrange to see them at the clinical research facility. If a potentially eligible patient is identified prior to detoxification from alcohol, an appointment will be made for after their detoxification. At the initial visit with the researcher and a medical doctor, the trial will be explained, written informed consent obtained, their eligibility assessed and baseline assessments completed. The site will take a full medical history at screening but will write to the GP to inform them of participation in the trial and the GP will be requested to inform us if they have any concerns about the patient participating in the trial. Once eligibility is confirmed, a date will be made for them to attend the study centre for their first treatment visit.

We will also set up a study website to accompany the study, where patients can register their interest and we will publicise the trial through forums and social networking, relevant charities such as Foundation 66, Alcohol Concern, newspaper, radio and TV, in advice centres, via word of mouth and face to face contact. All trial publicity advertisement as described here will be submitted and approved by the Research Ethics Committee.

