## 7 Study procedures and schedule of assessments

### 7.1 Informed consent procedure

It is the responsibility of the Investigator, or a person delegated by the Investigator to obtain written informed consent from each subject prior to participation in the trial, following provision of the trial participant's information sheet (PIS) and an adequate explanation of the aims, methods, anticipated benefits and potential hazards of the study. The person taking consent will be GCP and protocol trained, suitably qualified and experienced, and will have been delegated this duty by the CI/PI on the delegation log.

**At least 24 hours** will be given for consideration by the patient before taking part. The PI or delegate will record when the patient information sheet (PIS) has been given to the patient. The Investigator or designee will explain the patients are under no obligation to enter the trial and that they can withdraw at any time during the trial, without having to give a reason. No clinical trial procedures will be conducted prior to taking consent from the participant. Consent will not denote enrolment into trial. A second signed Informed Consent form will be given to the participant. The other original signed form will be retained at the study site in the site file and a copy placed in the medical notes. If new safety information results in significant changes in the risk/benefit assessment, the consent form will be reviewed and updated if necessary and subjects will be re-consented as appropriate. Re-consenting can be delegated to trial psychologists who have completed GCP training, protocol training and informed consent

training. All trial psychologists including research assistants and postdoctoral research associates can be delegated this task.

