## 7.2 Randomisation procedures

A blocked design for randomisation will be used to allocate patients using a 1:1:1:1 ratio for the 4 respective groups. Randomisation will be performed by a specialist company ([www.sealedenvelope.com](http://www.sealedenvelope.com)) who will hold the randomisation list and provide 24/7 internet access for unblinding services. Early drop-outs (during screening and the baseline week up until randomisation) will be replaced. Once patients have been randomised at week 0 they will not be replaced regardless of compliance or dropout status and will be analysed as part of the intention to treat analysis. After randomisation, the site research team will be given a unique trial randomisation code via email from [sealedenvelope.com](http://sealedenvelope.com). This code corresponds to an envelope at the site which contains the treatment allocation. These envelopes will be provided by the trial statistician at the start of the trial and are kept in a secure location by allocated partially unblinded staff. The trial statistician will be provided the treatment allocation codes prior to the start of the trial to prepare the envelopes. Separate envelopes will be provided for the delegated staff preparing the IMP (containing the IMP treatment allocation) and the psychology staff (containing the psychological treatment allocation). To protect the blind, pharmacy or delegated unblinded staff preparing the IMP at site will be notified separately via email of the randomisation code. An additional email is sent to the psychology team at site who can refer to the correct envelope to determine the psychological treatment allocation. Randomisation details of patients will be entered on a trial Subject Log and will follow the instructions set out in a Standard Operating Procedure (SOP) on randomisation. Data review will take place when half the target samples have been randomised. Upon randomisation, patients will be given a study specific patient card which will have study title, IMP details, patient ID and contact details of the out of hours contact in cases of emergency.

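### Concealment of the therapy allocation is not assured: ready-made therapy envelopes are held at site by a staff group that the documents also allow to recruit

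*SAP*

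**What the plan says.** SAP 4.3 has an independent provider generate the list of codes in advance, separately for each site. The codes go to the trial statistician, "who will generate two envelopes for each participant, one indicating the drug allocation and the other indicating the psychotherapy intervention". The two sets then part company. Drug envelopes go to the unblinded research nurse in Devon and the hospital pharmacist in London. For therapy: "The trial psychologists at each site will receive the psychotherapy allocation envelopes for the Devon and London sites".

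On timing and storage, Protocol 7.2 says: "These envelopes will be provided by the trial statistician at the start of the trial and are kept in a secure location". It describes the keepers as allocated staff who are partially unblinded.

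The trial anaesthetist performs the randomisation online (SAP 4.3). At that moment, "This trial ID number will be linked to the next available randomisation allocation code". An e-mail then tells the psychology team which envelope to consult (Protocol 7.2).

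On recruitment, Protocol 6 says: "The research fellow / assistant psychologist will then contact the individual interested in participating via phone". If the person is interested, the researcher will "then go through the prescreening questionnaire to establish whether the patient appears eligible to attend for a full screening appointment" and arrange the visit.

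Protocol 7.1, in the context of re-consenting, shows how widely the term trial psychologist is drawn: "All trial psychologists including research assistants and postdoctoral research associates can be delegated this task".

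**The concern.** Central randomisation protects against selection when nobody who influences entry can learn the next allocation. Here the web system releases the code only at visit 2, but the therapy that the code stands for has been on site since the start of the trial. The people who receive it belong to a group whose members may also phone, pre-screen and book.

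Therapy is the open factor. The psychologist delivers it and the participant knows it, so any advance knowledge would be about a treatment on which staff may hold views. Visit 2 may fall 1 to 28 days after screening, or later with a refresher visit, which leaves some room to influence the order of entry.

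Selection of this kind would bias the comparisons that turn on therapy. The SAP's adjustment for site would not remove it, because it would arise within a site. Calling the analyses exploratory answers low power and multiplicity, but not selection.

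**Working it through.** The plan gives no figure on this point, so the check sets the passages side by side.

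**1. How many allocations are on site in advance.** Protocol 13.2.1 plans 24 per cell in four cells: 24 × 4 = 96 participants. SAP 4.3 makes two envelopes each: 2 × 96 = 192, of which 96 are therapy envelopes. Before the first randomisation all 96 are unused; after *k* randomisations, 96 − *k* remain.

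**2. Who holds and who recruits.**

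| Task | Staff named | Source |
|---|---|---|
| Receive therapy envelopes | Trial psychologists at each site | SAP 4.3 |
| Keep envelopes | Allocated, partially unblinded staff | Protocol 7.2 |
| Deliver therapy | Trial psychologists | SAP 4.4 |
| Phone, pre-screen, book | Research fellow or assistant psychologist | Protocol 6 |
| Pre-screen | Delegated members of the research team | Protocol 7.4 |
| Trigger randomisation | Trial anaesthetist | SAP 4.3 |

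The first and fourth rows may describe the same people. Neither document says they do, and neither rules it out.

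**3. What reading ahead would require.** Three things must hold together:

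- a therapy envelope is read before the e-mailed code arrives;
- the envelopes are held in an order that matches the order in which codes are issued;
- the person who reads it can affect who is randomised next.

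If the first fails, holding the envelopes gives nothing away. If the second fails, opening one early does not identify the next allocation. If all three hold, the next therapy is known with certainty instead of being an even chance. The documents do not say whether envelopes are sealed, opaque or tamper-evident, how codes are ordered on them, or whether opening is logged.

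**4. Which analyses are exposed.** SAP 4.5 lists three comparisons.

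- Ketamine against placebo: not affected by this route. The drug envelopes go elsewhere, and the therapy envelope does not show the drug.
- Ketamine plus psychotherapy against ketamine plus psychoeducation: exposed. It is the planned contrast that addresses secondary objective 2.
- Ketamine plus psychotherapy against placebo plus psychoeducation: exposed in its therapy part only.

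**5. Effect of a change on the design.** None on size: 96 in total and 24 per cell stand.

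**The case against.** The plan has real safeguards. An independent provider generates the list. Randomisation follows confirmed eligibility and consent, and it is done by an anaesthetist blind to both factors. The code is e-mailed only afterwards. Envelopes are delivered securely and stored securely, and block sizes are withheld from sites. A reader might infer that therapy allocation is simply open to recruiters; these provisions do not support that. Early knowledge would need someone to break the procedure.

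The overlap of staff is also an inference. SAP 4.3 uses one term for those who receive therapy envelopes and another for those who recruit, and the wide description in Protocol 7.1 concerns re-consenting. This stands: overlap is permitted, not stated.

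Opportunity is limited too. Protocol 13.2.2 speaks of 96 participants over 24 months and of a 4-year recruitment period. Over two sites that is 96 / (24 × 2) = 2, or 96 / (48 × 2) = 1, per site per month. There will seldom be a queue to reorder. This reduces the likely harm without closing the route.

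A reader might also want to attach a bias in percentage points, or set one against the 25-point fall in relapse in Protocol 13.2.1. Neither is supported. Any such bias needs an assumed degree of steering and an assumed difference in risk, and the 25 points belong to ketamine against placebo, which this route does not touch. Guessing the next therapy from earlier ones in a block is a separate matter: it would arise in any blocked trial with an open factor, and removing the envelopes would not change it.

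Finally, the exposed contrasts are labelled exploratory, and all four arms are also reported descriptively, so secondary objective 2 does not rest on a single comparison. That lowers the stakes, but a selected contrast would still mislead the planning of a later trial.

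**Conclusion.** The point holds as a weakness in allocation handling: concealment of therapy is not assured, because advance allocations are placed with a group that may recruit and no separation of roles is stated. Its extent is 96 therapy envelopes and two of three planned contrasts, one of them only in part. No bias can be quantified from the documents, and there is no evidence that any envelope would be read early.

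The conclusion assumes that some envelope holders do take part in recruitment, which the documents allow but do not say. If the sponsor can show that holders and recruiters were different people throughout, or that envelopes were tamper-evident, not in code order and logged on opening, the concern falls away.

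**What to change.** Amend SAP 4.3 and Protocol 7.2 so that no therapy allocation is held at site before randomisation. The provider already e-mails the psychology team after each randomisation; have that message state the participant's therapy allocation, send it to that team only so that the anaesthetist stays blind to therapy, and withdraw the therapy envelopes.

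If paper must stay, give the therapy envelopes to someone with no part in recruitment, following the pattern of the drug envelopes, which go outside the psychology team. State how they are sealed, how codes are ordered and that each opening is logged.

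The cost is a small system configuration and test, plus the wording changes. No participants or staff are added, and the trial already relies on e-mail at visit 2. The change does not address guessing within blocks.

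The SAP's audit trail runs from June 2016 to March 2020, so enrolment may be well advanced, although the documents give no recruitment dates. In that case the change protects only those still to be randomised, and the sponsor should also record who held the therapy envelopes, who recruited, and how the envelopes were kept and opened.
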